#### **Study Synopsis**

The goal of this study is to determine the impact of an auditory training program on the function of the inner ear and auditory brainstem. In normal-hearing individuals, the medial olivocochlear (MOC) branch of the auditory efferent system appears to aid with hearing signals in noise. A previous study in young normal-hearing adults found that auditory training strengthened the function of the MOC system in some participants in a way that coincided with their improvements in perceiving speech sounds in background noise (de Boer and Thornton, 2008, *J Neurosci*, 28:4929-4937). The MOC function measured at baseline also predicted the amount of success from the auditory training. Although these results are promising, it is not known if they generalize to populations that often have hearing-in-noise problems such as older and hearing-impaired adults.

This study will examine how an auditory training program impacts MOC activity in a group of older adults with normal hearing or mild hearing loss. This is a prospective study utilizing a repeated-measures design. Participants will participate in a computerized auditory training program taking place over a maximum of one year. Transient-evoked otoacoustic emissions (TEOAEs) will be used to measure the strength of MOC activity at each visit. Performance on untrained stimuli (words and sentences) will also be measured. A control group (no auditory training) will also be used to establish test-retest reliability for TEOAE measurements and performance on the word and sentence testing. A second “speech” control group will only participate in speech testing and the TEOAE testing. The results of this study may contribute to the improved diagnosis and treatment of hearing-in-noise problems in Veterans and in the civilian population.

## **Test Site**

This is a single-site study that will take place at the Auditory Research Laboratory, located at the VA Loma Linda Healthcare System (VALLHS) in Loma Linda, CA.

## **Participants and Eligibility**

Veterans and non-Veterans, both males and females, between the ages of 35 and 89 with either normal hearing or mild sensorineural hearing loss will participate. Recruitment of non-Veteran participants is necessary because there is a high prevalence of hearing loss in the Veteran population, especially those 50 years of age and older

([http://www.publichealth.va.gov/docs/vhi/hearing\\_impairment.pdf](http://www.publichealth.va.gov/docs/vhi/hearing_impairment.pdf)). Past efforts by our laboratory to recruit a sufficient number of normal-hearing Veterans ages 35 and older have proven difficult. Women and minorities will be encouraged to participate.

We plan to screen up to 1000 participants. Up to 200 volunteers will be enrolled in the study. Each participant will participate in from 1 to 14 study visits.

The following exclusion criteria will apply: (1) a conductive hearing loss or other otologic pathology; (2) three-frequency pure-tone average >40 dB HL; (3) >15 dB asymmetry in hearing thresholds at more than two frequencies; (4) absent acoustic reflexes; (5) absent transient-evoked otoacoustic emissions (TEOAEs), defined as a signal-to-noise ratio of <6 decibels; (6) chronic disease or use of medication that might affect the auditory system or the participant's ability to perform the experimental tasks; (7) an inability to comply with test procedures; (8) an inability to read and speak English.

## **Participant Groups**

Participants will be randomly assigned *a priori* to either the Experimental group (auditory training) or Control group (no auditory training) using simple random assignment. Because the third group (Speech Group) is added after the experimental and control groups have completed their participation, to provide additional power to the regression analysis, the Speech group will be assigned by the investigator. Because this study will detect whether or not significant changes in MOC activity and speech perception across time occurred as a result of auditory training, the Control group is needed to establish the test-retest reliability of our outcome measures in the absence of any training. Participants will be informed of which group they are assigned to at the initial visit, but they will not be allowed to change groups.

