### **Instrumentation**

Standard-of-care screenings and experimental testing will be carried out in a double-walled sound-isolated audiometric chamber adjoined to a single-walled room in the Auditory Research Laboratory, located at the VALLHS. Initial audiometric testing using standard-of-care procedures will be conducted to verify eligibility for the study and will be carried out using standard clinical equipment. A Grason-Stadler (GSI 61) clinical audiometer calibrated to standards (American National Standards Institute, 1996) will be used to deliver the pure-tone signals for threshold testing through Etymotic Research ER-3A insert earphones. Speech audiometry will be achieved by presenting words (pre-recorded or live voice) through insert earphones via the audiometer. A Grason-Stadler Tymptstar Middle Ear Analyzer acoustic-immittance meter will be used for immittance measurements to verify normal middle ear function. A visual inspection of participants' ear canals and tympanic membranes will be performed using a Welch-Allyn otoscope.

Experimental tests will consist of TEOAE testing, word/sentence recognition testing, and an auditory training program (only participants in the Experimental group will undergo the auditory training). For all experimental testing, participants will be seated in the sound booth. TEOAE testing uses an Etymotic Research ER-10D microphone and loudspeaker assembly. The hardware is controlled by a computer-based otoacoustic emissions system (Intelligent Hearing Systems) that interfaces with the MATLAB programming language. The software allows for the selection of sounds, as well as parameters of the testing such as duration, amplitude, and rate of stimulus presentation. For word and sentence testing, pre-recorded speech stimuli (saved as digital computer files) are presented through insert earphones using custom MATLAB software. Participants will make responses either by

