### Experimental Procedures

The following experimental procedures will be conducted:

TEOAE Testing: The basic task of the participants is similar to TEOAE procedures used clinically to evaluate hearing function objectively. Testing involves listening to sounds presented through earphones while seated comfortably in a sound-treated booth, and remaining alert but quiet in order to successfully measure responses from the cochlea and brainstem. Excessive body movement, swallowing, coughing, talking, and chewing creates acoustic and electric noise that can obscure recordings of TEOAEs, so it is imperative that participants remain as still as they can during the measurements. The experimental measurements differ from clinical measurements primarily in the types of sounds presented, the data analysis, and the use of an attention task to keep participants alert and awake. Specially constructed stimuli intended to stimulate the MOC system will be generated digitally on a computer, and played out to the listener using high-quality digital-to-analog converters, attenuators, filters, and other laboratory equipment. These sounds involve amplitude-modulated tones, click trains, and white noise. All stimuli will be presented at moderate volumes that are well below sound levels considered hazardous by OSHA and NIOSH standards. TEOAE measurements consist of waveforms, which are changes in sound amplitude across time. MOC function will be quantified as the change in waveform amplitude with versus without white noise presented to the opposite ear, where a larger change indicates stronger MOC activity. Repeated measurements will be obtained (both within a study visit and across study visits) to determine the change in MOC activity across time. Immittance audiometry will be obtained immediately prior to TEOAE testing at each visit to ensure that middle ear function is normal (successful measurement of TEOAEs requires normal middle ear function).

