Word/Sentence Testing: Testing involves listening to words and sentences presented through earphones while seated in the sound-treated booth. Speech stimuli will be presented in the presence of background noise. Participants make a response about the word(s) they heard. For word testing, participants press a button on a touch screen monitor corresponding to the words that they heard. Their responses are automatically recorded by custom software. For sentence testing, participants verbally repeat back the words they hear in each sentence. The experimenter enters the number of correct responses into the computer. The experimental measurements differ from clinical measurements primarily in the types of sounds presented and the data analysis. Sounds will be presented at safe and comfortable levels. Performance will be quantified as the number of words correct and also the characteristics of the stimuli (e.g., the levels of the speech and background noise). Repeated measurements will be obtained (both within a study visit and across study visits) to determine the change in speech perception ability across time.

Auditory Training (Experimental group only): Listeners will be seated comfortably in the sound booth at a workstation with a computer screen, keyboard, and mouse. Sounds will be presented to the participants through insert earphones. Sounds for the testing and training will be presented at calibrated levels from the computer. Participants will make their responses concerning what they heard by mouse click or keyboard entry. At the end of each

session, the response data will be stored on the local computer. No patient identifiable information will be included on the data files. Performance will be quantified as the number of correct responses and also the characteristics of the stimuli (e.g., the levels of the speech and background noise). The auditory training program consists of a curriculum of word and sentence presentations in various noise levels, and performance on repeated measurements are tracked throughout the subject's participation in the program.

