All participants will undergo otoscopy, immittance testing, TEOAE testing, word testing, and sentence testing at each visit. Participants in the experimental group will also complete the auditory training program, with baseline (pre-training) measures at visit 1, training occurring in visits 2-11, and visit 12 serving as the retention (post-training) measurements. These participants will therefore undergo a total of 15 hours of auditory training spread across 10 visits, plus pre- and post-tests. Pure-tone audiometry will be repeated for all participants at visits 6, 11, and 12 to detect any significant changes in hearing thresholds during the course of a participant's participation (not due to actual participation in the study because all sound levels will be presented at safe volumes). Such changes in audiometric measures are not likely to occur over this relatively short time period. All participants (except those in the Speech group) will be asked to return for a visit twice a week for the first 6 weeks (visits 1-11) and return for the final visit 4 weeks later (visit 12). Each subject will be allowed a maximum of two make-up visits in case a visit needs to be stopped early, resulting in a maximum of 14 study visits.

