### **Data Analysis**

Correlational analyses will be used to determine the correspondence between changes in MOC activity and changes in speech perception during the course of auditory training. Statistical analyses of test-retest reliability from the Control group data will be used to determine what constitutes a statistically significant change in MOC activity and speech perception ability. Repeated measures analyses of variance (both within a study visit and across study visits) will also be performed.

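### Does the late Speech group need its regression, size and visit schedule written into the plan before it can serve its stated purpose?

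*Combined protocol and SAP*

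**What the plan says.** The documents describe the Speech group in three places.

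- **Participant Groups:** it "is added after the experimental and control groups have completed their participation, to provide additional power to the regression analysis". The investigator assigns its members; the Experimental and Control groups are randomised.
- **Study Synopsis:** this second "control group will only participate in speech testing and the TEOAE testing".
- **Order of Procedures:** "All participants (except those in the Speech group) will be asked to return for a visit twice a week". The Speech group is exempt from that timetable and receives no other. The same section says: "All participants will undergo otoscopy, immittance testing, TEOAE testing, word testing, and sentence testing at each visit".

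Data Analysis lists three things: correlations for the "correspondence between changes in MOC activity and changes in speech perception during the course of auditory training", test-retest analysis of the Control data, and repeated-measures analysis of variance within and across visits. It uses no form of the word regression and does not name the Speech group. Instrumentation states that "only participants in the Experimental group will undergo the auditory training".

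On numbers, Sample Size requires at least 12 trained participants and plans up to 40 in total, 20 in each of the first two groups. Participants and Eligibility caps enrolment at 200 and allows 1 to 14 visits per person. Neither section gives a Speech group figure.

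**The concern.** Power for the regression is the only reason given for recruiting the Speech group, so a reader looks for that regression in Data Analysis and does not find it. Treating regression as loose wording for correlation does not help on a literal reading. The planned correlation is of changes during training, and the Speech group is untrained and has no stated repeat visits from which to form a change.

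If that were the whole story, people would be recruited for a power gain that cannot occur. There is also a worry about flexibility. Word and sentence tests are both collected, no covariates are named, and the group joins after the other two have finished. The outcome and model might then be chosen with earlier data in view. Ages run from 35 to 89 and hearing from normal to mild loss, so an unadjusted association at one visit could partly reflect age or threshold.

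**Working it through.** **1. Which analyses can the Speech group enter?** The sections set side by side:

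| Analysis | Source | Needs | Speech group |
|---|---|---|---|
| Correlation of changes during training | Data Analysis | training and repeat visits | not as worded |
| Test-retest reliability | Data Analysis | Control data | no |
| Repeated-measures ANOVA | Data Analysis | repeated measurements | not stated; within-visit repeats possible |
| The regression | Participant Groups | not stated; one visit is enough if cross-sectional | yes, by its stated purpose |

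For the last row the measurements exist. Experimental Procedures defines the predictor ("MOC function will be quantified as the change in waveform amplitude with versus without white noise presented to the opposite ear") and the speech tests (for example, "For sentence testing, participants verbally repeat back the words they hear in each sentence"). One visit gives one pair of values per person.

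**2. The plan's own figure.** The minimum of 12 is the largest of 10 (MOC), 12 (words) and 11 (sentences), each for a paired pre/post difference at 0.05 with 80% power. The means and standard deviations are not printed, so it cannot be reproduced. Solving backwards for n = 12, two-sided (the plan does not state sidedness), gives a standardised paired difference of 0.889 by the noncentral t. The normal approximation gives (1.960 + 0.842)/√12 = 0.809. The Speech group plays no part in this calculation.

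**3. The association, with and without the Speech group.** The smallest correlation detectable with 80% power at two-sided 0.05 is tanh[(1.960 + 0.842)/√(n − 3)].

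- Training-change correlation, n = 12: tanh(2.802/3.000) = 0.73.
- Training-change correlation, n = 20: tanh(2.802/4.123) = 0.59.
- One-visit association, n = 40: tanh(2.802/6.083) = 0.43.
- One-visit association, n = 60 (20 Speech participants, an assumption): tanh(2.802/7.550) = 0.355.

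The first two do not move however many Speech participants join. The last two show a real gain.

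**4. The same gain with two covariates.** Power is Φ[atanh(r)·√(n − 5) − 1.960], where r is an assumed partial correlation. At r = 0.4, atanh(r) = 0.4236.

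- n = 40: 0.4236 × 5.916 − 1.960 = 0.546, power 0.708.
- n = 60: 0.4236 × 7.416 − 1.960 = 1.182, power 0.881.

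| Assumed r | Power, n = 40 | Power, n = 60 | Total n for 80% | Beyond 40 | Beyond 24 |
|---|---|---|---|---|---|
| 0.3 | 0.449 | 0.631 | 87 | 47 | 63 |
| 0.4 | 0.708 | 0.881 | 49 | 9 | 25 |
| 0.5 | 0.901 | 0.983 | 32 | 0 | 8 |

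Total n is [2.802/atanh(r)]² + 5, rounded up. The base of 24 is the minimum of 12 in each of the first two groups. The enrolment cap leaves 200 − 40 = 160 places beyond the planned 40, or 200 − 24 = 176 beyond the minimum, so every number in the table fits within it.

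**The case for a change.** The case for a change is that a group whose only justification is power should be tied to a named model and a fixed number. On the literal wording of Data Analysis it adds nothing to the one MOC–speech association described there. Writing the model down would take a few sentences, and nothing new would have to be measured.

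Part of this stands. The two sections do not meet. The training-change correlation stays at 12 to 20 people, and the claimed power cannot be checked from the documents.

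The rest is weaker.

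- Saying the Speech group can enter no analysis goes too far. Participant Groups already commits to a regression that includes it, and Order of Procedures removes the twice-weekly timetable without ruling out repeat visits.
- Participant Groups gives the timing of recruitment, not of analysis. A model chosen after looking at data is possible, but the text does not show it.
- Investigator assignment is disclosed, and an association at one visit does not need randomisation.
- Date of birth and hearing screening results are collected, so adjustment for age and hearing level is open to any analyst. Concern about an unadjusted model is about a model the plan does not propose.
- The spread in the number needed (47, 9 or 0 beyond 40) comes from varying an assumed correlation; it does not measure an error in the plan.

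**Conclusion.** No change is called for. Data Analysis omits the regression that Participant Groups refers to, along with the Speech group's size and visits. This is missing detail in a supplementary analysis, and no stated figure or rule is shown to be wrong. The natural reading is a cross-sectional regression of speech-in-noise performance on MOC activity, and under it the stated reason for the group holds: power rises from 71% to 88% between 40 and 60 participants at an assumed partial correlation of 0.4. Prescribing the visit, covariates and outcomes from outside would be a guess at what the investigators meant, and they can fill it in sensibly.

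The paired pre/post comparison that sets the sample size and the Control reliability analysis are untouched. The training-change correlation keeps the same 12 to 20 participants it would have had without the Speech group. The conclusion rests on the regression being cross-sectional and on each Speech participant giving at least one visit with both TEOAE and speech tests. The power figures also assume the correlations, the two covariates and the total of 60, none of which the documents give.

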## **Sample Size**

Based on power analyses, the study will require participation of at least 12 participants in the experimental group. Sample sizes were estimated using data from studies that reported differences in MOC activity or speech perception before and after an auditory training program. Pre- and post-training means and standard deviations were used to compute the minimum sample sizes ( $n$ ) needed to detect a mean difference in paired samples (i.e., mean results for pre- versus post-training performance in the same participants), using methods described in Dupont and Plummer (1990, *Control Clin Trials*, 11:116-128). Sample sizes were calculated using a type I error rate of 0.05 and 80% power to detect differences in mean performance between pre-training and post-training. For MOC activity, the results of de Boer and Thornton (2008, *J Neurosci*, 28:4929-4937) indicated a minimum of  $n = 10$ . For word recognition, the results of Henshaw and Ferguson (2014, *Proc ISAAR 2013*) indicated a minimum of  $n = 12$ . For sentence recognition, the results of Song et al. (2011, *Cereb Cortex*, 22:1180-1190) indicated a minimum of  $n = 11$ . An

equal number of participants will be assigned to the control group. To account for possible subject attrition, we tentatively plan to recruit up to 40 total participants (20 each in the Experimental and Control groups).

### **Recruitment**

Potential participants will be recruited through several methods. One method will include a contact list of current and former participants of the Auditory Research Laboratory who agreed to be contacted regarding future studies. This [REDACTED] is stored on [REDACTED] and is password-protected so only authorized study staff has access. Personal information stored on this list consists of first and last name, date of birth, last 4 numbers of the SSN, phone number, and results of the hearing screening conducted during their participation in an earlier study. Potentially eligible participants from this list will be contacted by phone. Information about the study will be discussed and if they are interested, an initial study visit will be scheduled at their convenience.

Other recruitment methods include electronic billboard advertisements placed throughout the VALLHS, volunteer fliers placed in the VALLHS audiology clinic, word-of-mouth referral from VALLHS audiologists, and special events held on VALLHS property such as health fairs and research events.

For all forms of recruitment, interested individuals will be provided the laboratory phone number to call if they are interested. The research team will describe the study in more detail and answer any questions the individual may have. If they continue to be interested, the research team will conduct an initial screening over the phone. Individuals will provide their first and last name and last 4 of the SSN to authorized study staff. This information will be stored in the [REDACTED] password-protected document stored on [REDACTED] accessible only to authorized study staff. Authorized study staff will ask the individual a series of questions related to the inclusion and exclusion criteria for this study. They will be asked if they are between ages 35-89, have normal hearing or mild hearing loss, have the ability to read and speak English, have no history of conductive hearing loss or otologic pathology, and have no chronic disease or use of medication that affects the auditory system or ability to perform experimental tasks. The answers to these questions will not be stored in the screening log, but are used solely to determine if the person is eligible for an initial study visit. For individuals who have had a previous hearing test at the Loma Linda VA, this information will be accessed in CPRS by authorized study staff to determine if the individual's hearing thresholds fall within the inclusion criteria. If the test indicates that their hearing falls within the allowable range, a laboratory visit will be scheduled if they are interested in being in the study. If the individual has not had a hearing test at the Loma Linda VA but reports normal hearing or mild hearing loss, an initial visit will be scheduled at the individual's convenience.

